6.11.1.2 Primary Efficacy Analysis

A restricted maximum likelihood (REML)-based mixed model for repeated measures (MMRM) will be utilized to analyze the change from baseline to Week 12 in the weekly mean of the NRS score assessing average pain intensity related to DPN in the past 24 hours.

The MMRM model will have site, treatment group, week, baseline NRS score, and treatment-by-week interaction as terms in the model. The unstructured covariance (UN) will be utilized as the within-subject covariance structure in the event that the model fails to converge using the UN, the covariance structure among Toeplitz (TOEP), first-order autoregressive [AR(1)], and compound symmetry (CS) for which the model converges and yields the least corrected Akaike's information criterion (AICC) will be used. The Kenward-Roger degrees of freedom correction will also be used for this analysis.

The estimate of the treatment difference at Week 12 and standard error (SE) will be derived from this model. Observed NRS scores at baseline and at each week, as well as their change from baseline at each week will be presented by treatment group. The LS means, corresponding SEs, and 95% CI for each treatment group, as well as the estimate, corresponding SE, and p-value of the treatment difference in LS means at each week will be presented.

The following is the sample SAS code that will be used for this analysis:

```
PROC MIXED DATA= DATAIN;

CLASS USUBJID TREATMENT WEEK SITE;

MODEL CFB = TREATMENT WEEK SITE TREATMENT*WEEK BASELINE / DDFM=KR;

REPEATED WEEK / SUBJECT=USUBJID TYPE=UN;

LSMEANS TREATMENT*WEEK / CL DIFF;

RUN;
```

A line plot showing the LS means and 95% CIs of the weekly mean NRS scores from Week 1 through Week 12 for each treatment group will be presented.

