4 SAMPLE SIZE

The planned sample size is a total of 204 randomized subjects. This will provide approximately 80% power to detect a difference in means of 0.73 assuming that the common standard deviation is 1.7 (and accounting for 15% drop-out rate), using two-sided statistical testing with an overall Type I error rate of 0.05.

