5 RANDOMIZATION

Pain scores reported by subjects during the Screening Period will be evaluated by the Interactive response technology (IRT) system for raw score and for variability among scores after transmission of pain scores from the handheld devices to determine randomization eligibility. Subjects whose mean of the daily average pain intensity score during the preceding seven (7) days is within the protocol-defined algorithm and whose compliance with daily diary completion is adequate will be eligible for randomization. The absolute pain scores and variability among scores, as well as the actual percentage required for diary compliance, will be masked to investigators and subjects. Subject eligibility for randomization into the study based on these variables will be communicated to the investigator via the IRT system. The IRT system will notify the site if the subject is "Eligible" or "Not eligible." No other information will be provided.

Eligible subjects will be randomized to receive either NYX-2925 50 mg or placebo daily in a 1:1 allocation.

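### The primary MMRM fits one baseline slope for all 12 weeks; if the slope varies by week, the Week 12 contrast may lose a little precision, which a baseline-by-week term would recover

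*SAP*

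**What the plan says.** The fixed effects in SAP 6.11.1.2 are "site, treatment group, week, baseline NRS score, and treatment-by-week interaction as terms in the model". The sample code agrees: "MODEL CFB = TREATMENT WEEK SITE TREATMENT*WEEK BASELINE / DDFM=KR", with "REPEATED WEEK / SUBJECT=USUBJID TYPE=UN" for the within-subject covariance. Baseline therefore enters once, with no interaction with week. The protocol's model (Synopsis, Statistical methods; Section 12.6.1.1) has the same terms. Neither document says why the interaction is left out.

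The hypothesis (SAP 6.11.1) and the population-level summary (SAP 6.11.1.1) concern Week 12 alone. The same model is refitted after imputation (SAP 6.11.1.3.1). It is adapted, with the matching baseline covariate, for DSIS (6.11.2.1) and the QOL-DN total score (6.11.2.4). The supportive ANCOVA (6.11.1.4.1) uses Week 12 change only.

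On size, SAP Section 4 states: "The planned sample size is a total of 204 randomized subjects". The target it sets for that number is "approximately 80% power to detect a difference in means of 0.73". Behind it lie an SD of 1.7, 15% dropout and a two-sided test at 0.05. SAP Section 5 says subjects are "randomized to receive either NYX-2925 50 mg or placebo daily in a 1:1 allocation".

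**The concern.** The model lets the treatment effect differ at every week and leaves the 12 x 12 covariance unstructured, yet it holds the baseline slope constant. If the relation between change and baseline pain shifts during treatment, the fitted slope is a weighted average over weeks. The week that carries the primary test is then adjusted with the wrong slope.

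The consequence is that chance baseline imbalance is only partly removed at Week 12. With complete data, that is the same thing as a larger variance for the Week 12 contrast; the two are one effect, not two. Planned power is only about 80%, so even a small avoidable loss is worth recovering if the remedy costs almost nothing.

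The SAP also treats baseline differently elsewhere. The ANCOVA estimates a Week 12 slope of its own, and the sequential imputation regressions let baseline's contribution vary by week. A gap between the primary and the other results could partly reflect this difference rather than missing data.

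**Working it through.** **Inputs from the SAP.** 204 randomised, 1:1, difference 0.73, SD 1.7, 15% dropout, two-sided 0.05.

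**Inputs assumed.** Weekly slopes, baseline SD, Week 12 residual SD where 1.6 is used, and correlations. None is in the documents.

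**1. The planned figure reproduces.**
- n per arm = 2(1.960 + 0.842)² x 1.7² / 0.73² = 85.1, so 86 (172 evaluable).
- 86 / 0.85 = 101.2, so 102 per arm and 204 in total.
- With 204 x 0.85 / 2 = 86.7 evaluable per arm: 0.73 / (1.7 x √(2/86.7)) = 2.827, and Φ(2.827 − 1.960) = 80.7% power.

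**2. Cost of a common slope.** With complete data and free treatment-by-week means, the Week 12 estimate is the difference in mean change minus slope x baseline imbalance. Using a common slope bc in place of the Week 12 slope b12 multiplies the variance by

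1 + (b12 − bc)² x SD_baseline² / SD_residual².

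With assumed baseline SD 1.1 and residual SD 1.6, where subjects = 204 x (1 − 1/ratio) and power = Φ(2.827/√ratio − 1.960):

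| Slope gap | Variance ratio | Subjects of 204 | Power |
|---|---|---|---|
| 0 | 1.000 | 0 | 80.7% |
| 0.15 | 1.011 | 2 | 80.3% |
| 0.20 | 1.019 | 4 | 80.0% |
| 0.30 | 1.043 | 8 | 79.1% |

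With baseline SD 0.8 instead, gaps of 0.15 to 0.30 give 0.6% to 2.3%.

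**3. Where the common slope settles.** When variance grows over time under an unstructured covariance, the weighting favours the early weeks. With slopes running from −0.1 to −0.5, the common slope is about −0.11, so the misfit is greatest at Week 12. Taking Week 12 SD 1.7, baseline SD 0.8 to 1.5 and three assumed correlation patterns:

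| Slope, Week 1 to Week 12 | Variance increase | SE increase | Power |
|---|---|---|---|
| constant −0.2 | 0% | 0% | 80.7% |
| −0.1 to −0.3 | 0.8-3.2% | 0.4-1.6% | 79.5-80.4% |
| −0.05 to −0.35 | 1.9-7.3% | 0.9-3.6% | 77.9-80.0% |
| −0.1 to −0.5 | 3.3-12.9% | 1.7-6.3% | 75.8-79.4% |

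Example cell: slopes −0.1 to −0.3, baseline SD 1.2, bc = −0.106. Then 1 + (0.194 x 1.2)² / 1.7² = 1.019.

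**4. Simulation.** Unstructured MMRM, 102 per arm, site omitted, 400 runs per scenario, with no dropout or about 15-20% dropout that is missing at random. The ratio of Week 12 SEs, SAP model over model with baseline-by-week, was 0.99-1.00 with a constant slope, 1.00-1.03 for the two intermediate slope changes, and 1.04-1.08 for −0.1 to −0.5 with baseline SD 1.5.

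**5. The same effect as residual imbalance.** One standard error of baseline imbalance is 1.1 x √(2/102) = 0.154. A slope gap of 0.15 to 0.30 leaves 0.02 to 0.05 NRS points unadjusted, or 3-6% of 0.73.

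**The case against.** The strongest reply is that nothing in the documents shows the slope changing. No weekly slopes, baseline SD or Week 12 residual SD are given, and the idea that slopes steepen over time is general experience. That stands: the range must start at zero and the point must be conditional. Eligibility also requires baseline mean pain within a masked algorithm (Protocol 12.2, SAP Section 5), which may narrow the baseline spread and shrink the loss.

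Parsimony is a legitimate choice, and SAP 6.2.16 names convergence as a worry. But that worry concerns small sites, and the fallback in 6.11.1.2 concerns the covariance, which already has 78 parameters. Eleven more fixed effects are a minor addition. With a constant slope, the simpler model gained at most about 1% of the SE in simulation, within noise.

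The supportive ANCOVA does estimate its own Week 12 slope. That is a partial answer: it is not the primary test, and it uses only subjects with Week 12 data.

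A reader might go further and infer that the primary estimate is biased or its Type I error inflated. The documents do not support this. In simulation the Week 12 estimate was unbiased under both models without dropout, and when baseline-related dropout acted alike in both arms. The SAP model's estimate shrank only when that dropout was made to run in opposite directions by arm: from about −0.74 to −0.68 with slopes −0.1 to −0.3, and to −0.55 in the most extreme case. Nothing in either document suggests such a pattern.

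**Conclusion.** The point holds as a conditional, minor loss of efficiency. The omission is plain in both text and code. Its cost is nil if the slope is constant. For modest slope changes it is about 0-4% of Week 12 variance, equivalent to roughly 0-8 of 204 subjects and 0 to 1.6 power points. Losses beyond that need a stronger slope change or a wide baseline spread. These figures rest on assumed slopes, SDs and correlations.

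The sample size of 204 is unaffected, and randomisation keeps the primary test valid; Type I error is not at issue. It would also be too strong to say that the simpler model has no merit: it saves parameters, though the gain is negligible.

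**What to change.** Before unblinding, add `BASELINE*WEEK` to the MODEL statement and the list of terms in SAP 6.11.1.2. Make the same change in the models that reuse it with a baseline covariate: the post-imputation MMRM (6.11.1.3.1), and so the tipping-point analysis that refers back to it, DSIS (6.11.2.1) and QOL-DN (6.11.2.4). The PGI-C and acetaminophen-dose models have no baseline covariate and need no change.

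Record the addition in SAP Section 9, because it departs from the protocol's model. Made after unblinding, it would be post hoc.

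The cost is 11 extra fixed-effect degrees of freedom in the 12-week models and 1 for QOL-DN, which has two post-baseline visits. No new data are needed, and the loss is negligible if the slope turns out to be constant.

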6.2.16 Pooled Sites

The study protocol indicates that study site will be included as factor in statistical models. It was further indicated that the study can include up to 37 study sites in the United States. It is likely that some of these sites will have small numbers of subjects included in the mITT population, which could lead to convergence issues, unreliable treatment effect estimates and p-values. Thus, in the event that there are study sites with fewer than 6 subjects included in the mITT population, these sites will be pooled together to form a single site, such that the pooled sites will have a minimum of 6 subjects included in the mITT. The resulting pooled sites (referred to as "site" from here on) will be used in the analyses.

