The following is the sample SAS code that will be used to implement the control-based pattern mixture imputation:

```
PROC MI DATA=DATAIN OUT=DATAIN_MONO SEED=373613962 NIMPUTE=1;
BY TREATMENT;
VAR BASELINE NRS_Week1-NRS_Week12;
MCMC CHAIN=MULTIPLE IMPUTE=MONOTONE PRIOR = JEFFREYS;
RUN;
PROC MI DATA= DATAIN_MONO SEED=373613962 NIMPUTE=20
OUT=DATA_IMPUTED;
CLASS TREATMENT SITE;
MONOTONE REG(NRS_Week1-NRS_Week12);
MNAR MODEL(NRS1_Week1-NRS_Week12 /
MODELOBS=(TREATMENT='Placebo'));
VAR SITE BASELINE NRS_Week1-NRS_Week12;
RUN;
```

Once all the weekly mean NRS scores are imputed, the change from baseline at each week will be calculated and consequently will be analyzed using the same MMRM model employed in the primary analysis.

The following sample SAS code will be used:

```
PROC MIXED DATA= IMPUTED_ALL;

BY _IMPUTATION_; /* 20 sets of results produced */

CLASS USUBJID TREATMENT WEEK SITE;

MODEL CFB = TREATMENT WEEK SITE TREATMENT*WEEK BASELINE /

DDFM=KR;

REPEATED WEEK / SUBJECT=USUBJID TYPE=UN;

LSMEANS TREATMENT TREATMENT*WEEK / CL DIFF;

ODS OUTPUT LSMEANS=LSMEANS DIFFS=DIFFS;

RUN;
```

Then the results are to be summarized using PROC MIANALYZE, where the treatment group LS means and their differences between treatments will be combined across all 20 imputed datasets:

```
PROC SORT DATA= LSMEANS; BY TREATMENT WEEK _IMPUTATION_; RUN;

PROC MIANALYZE PARMS= LSMEANS;

MODELEFFECTS ESTIMATE;

STDERR STDERR;

ODS OUTPUT PARAMETERESTIMATES= LSMEANS_COMB;

BY TREATMENT WEEK;

RUN;

PROC SORT DATA= DIFFS; BY TREATMENT;

RUN;

PROC MIANALYZE PARMS= DIFFS (WHERE=(WEEK=_WEEK));

MODELEFFECTS ESTIMATE;

STDERR STDERR;

ODS OUTPUT PARAMETERESTIMATES= DIFFS_COMB;

BY TREATMENT;

RUN;
```

LS means, SEs, and 95% CIs for each treatment group based on the imputed data will be presented at each week as well as the estimate of treatment difference, SE, and p-value at each week with Week 12 as the primary timepoint of interest.

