6.11.1.3.2 Tipping Point Analysis

If the primary efficacy analysis in Section 6.11.1.2 significantly favors NYX-2925, a tipping point sensitivity analysis⁴ for the primary efficacy endpoint will be conducted to investigate how severe

the departure from the MAR assumption data must be to overturn conclusion from the primary analysis.

In this analysis, the assumption will be that that missing data in the NYX-2925 group follows a MNAR pattern. A tipping point-based approach will be used such that the trajectories of the subjects in the NYX-2925 group after early withdrawal are assumed to be worse than placebo by a fixed amount (δ). The value of δ is the adjustment added during imputation to the change from baseline NRS scores at each visit after study discontinuation. This increment is added only to the imputed change from baseline NRS scores at visits after study discontinuation of the subjects in NYX-2925. The value of δ will increase in increments of 0.1 (i.e., 0.1, 0.2, 0.3) up to the point at which the treatment difference at Week 12 is no longer statistically significant. This analysis provides a measure of the degree by which the subjects in the NYX-2925 group who discontinued early would need to be worse at each post-discontinuation visit in order for the null hypothesis of no treatment difference to no longer be rejected. Each imputed dataset produced through PROC MI procedure will be processed as follows:

- All values imputed for the placebo group will remain unchanged
- All values imputed for the NYX-2925 group will be incremented by a value of δ, which will vary from 0 up to a value by which statistical significance is not reached
- The modified data will be analyzed using similar analysis as described in Section 6.11.1.

Results will then be combined using PROC MIANALYZE and will consequently be recorded.

The "tipping point" is defined as the value of δ at which the result changes from statistically significant treatment effect to a treatment effect that is no longer statistically significant. The larger the value of δ , the more robust the conclusion from the primary analysis, with respect to assumptions around missing data.

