6.11.1.4 Supportive Analysis

6.11.1.4.1 Analysis of Covariance on change from baseline to Week 12 in the weekly mean of the NRS score assessing average pain intensity related to DPN in the past 24 hours

To assess the robustness of the result observed for the primary endpoint, an Analysis of Covariance (ANCOVA) model with site and treatment as factors, and baseline NRS score as a covariate will be employed as a supportive analysis.

[figure not shown]
The following is the sample SAS code that will be used to implement this analysis:

```
PROC MIXED DATA= DATAIN;
CLASS TREATMENT SITE;
MODEL CFB_WEEK12 = TREATMENT SITE BASELINE / SOLUTION;
LSMEANS TREATMENT / CL DIFF;
RUN;
```

The LS means, SEs, and 95% CIs will be provided for each treatment group, as well as treatment difference estimate, SE, and p-value at Week 12.

Page 36 of 57

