6.11.2 Secondary Endpoints

All secondary endpoints will be analyzed using the mITT population. The secondary endpoints of this study are as follows:

6.11.2.1 Change from baseline in the weekly mean of the Daily Sleep Interference Scale (DSIS) scores at Week 12

A similar approach in modeling the REML-based MMRM as in the primary analysis will be applied to the change from baseline in the weekly mean of the DSIS scores at Week 12 except that the outcome variable will be change from baseline in the weekly mean of the DSIS scores at Weeks 1 through 12, and the fixed effects are as follows: site, treatment group, week, baseline DSIS score, and treatment-by-week interaction as terms in the model. Observed NRS scores at baseline and at each week, as well as the change from baseline NRS scores at each week will be presented by treatment group. The LS means, corresponding SEs, and 95% CIs for each treatment group will also be presented at each week. Additionally, the estimate, corresponding SE, and p-value of the treatment difference at Week 12 will also be presented.

Subgroup analyses as described in Section 6.11.1.5 may also be performed for this endpoint.

6.11.2.2 Percentage of subjects 'much improved' or 'very much improved' on the Patient Global Impression of Change by Visit

The number and percentage of subjects reporting each of the response levels will be summarized by treatment for Weeks 4, 8, and 12.

Analysis will utilize the Cochran-Mantel-Haenszel (CMH) test to compare the treatment groups, using the following SAS code:

```
PROC FREQ DATA=CMHDATA1;
TABLES TREATMENT*RESP / RISKDIFF CMH;
ODS OUTPUT RISKDIFFCOL2 = RISK CMH = CMH_PVAL;
RUN:
```

The number and percentage of subjects 'much improved' or 'very much improved' by treatment at each visit will be presented. The risk difference for NYX-2925 vs placebo, corresponding 95% CI and p-value for the CMH statistic also be provided by visit.

Summary statistics for the PGI-C as a continuous score will also be provided by treatment group at each visit. Scores will be analyzed using the same REML-based MMRM as in the primary analysis, except with the exclusion of a baseline covariate.

Observed scores at each week (4, 8, and 12) will be presented by treatment group. The LS means, corresponding SEs, and 95% CIs for each treatment group will be presented at each week along with the LS mean difference, corresponding SE, and p-value.

A listing of all PGI-C scores will also be provided.

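### If the unstructured covariance fails to converge, every fallback in the SAP assumes equal variance over the 12 weeks, so the Week 12 standard error could be wrong; listing heterogeneous structures first is a cheap protection (minor, conditional)

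*SAP*

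**What the plan says.** The primary test is the Week 12 treatment difference from a REML-based MMRM on 12 weekly changes from baseline, with Kenward-Roger degrees of freedom (SAP 6.11.1.2). UN is the planned structure. If it fails to converge, the SAP uses "the covariance structure among Toeplitz (TOEP), first-order autoregressive [AR(1)], and compound symmetry (CS) for which the model converges" and which "yields the least corrected Akaike's information criterion (AICC) will be used". No heterogeneous version of these structures and no empirical standard error is listed. The protocol (12.6.1.1) names the MMRM but no covariance structure.

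The only variability figure is in SAP 4, where the trial is sized for "a difference in means of 0.73 assuming that the common standard deviation is 1.7", with 15% drop-out. No week-specific SD is given.

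Other analyses reuse the model:
- The pattern-mixture data "will be analyzed using the same MMRM model employed in the primary analysis" (6.11.1.3.1).
- For the tipping point, "The modified data will be analyzed using similar analysis as described in Section 6.11.1" (6.11.1.3.2).
- For sleep interference, "the REML-based MMRM as in the primary analysis will be applied to the change from baseline in the weekly mean of the DSIS scores" (6.11.2.1).
- Weekly acetaminophen dose follows the same approach (6.11.2.5).
- The table list in SAP 11 also shows MMRMs for pain upon walking and worst pain, and exploratory and subgroup MMRMs.

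**The concern.** TOEP, AR(1) and CS differ in how correlation falls with the gap between weeks, but each has one variance for all weeks. AICC can pick the best correlation shape of the three; it cannot pick a feature that none of them has. Kenward-Roger allows for uncertainty in the estimated covariance parameters but takes the structure itself as correct. Under the fallback, the Week 12 standard error therefore rests on a variance averaged over weeks.

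Unequal variance is plausible. The response is adjusted for baseline, and if a subject's score becomes less correlated with baseline over time, the residual variance grows. The Week 12 p-value and confidence interval would then be too favourable. If variance shrinks instead, power is lost. The reuse of the model would carry the same error into the other analyses if they too fell back.

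**Working it through.** **1. The plan's own figure.** Inputs from SAP 4: difference 0.73, SD 1.7, two-sided 0.05, about 80% power, 15% drop-out.

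n per arm = 2 × (1.96 + 0.8416)² × 1.7² / 0.73² = 85.1, so 86. Then 86 / 0.85 = 101.2, so 102 per arm and 204 in total. This reproduces the SAP and is not affected by the present point.

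**2. Parameter counts for 12 weeks.** UN: 12 × 13 / 2 = 78. TOEP 12, AR(1) 2, CS 2. The heterogeneous versions add 11 each: TOEPH 23, ARH(1) 13, CSH 13.

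**3. Complete-data approximation.** Assumption, not in the documents: the weekly residual SD moves linearly from a Week 1 value to 1.7 at Week 12. With one variance for all weeks,

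ratio = reported SE / true SE ≈ √(mean weekly variance) / 1.7, and actual type I error = 2Φ(−1.96 × ratio).

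| Week 1 SD | Mean variance | Square root | Ratio | Type I error |
|---|---|---|---|---|
| 1.1 | 1.995 | 1.413 | 0.831 | 10.3% |
| 1.4 | 2.411 | 1.553 | 0.913 | 7.3% |
| 1.7 (flat) | 2.890 | 1.700 | 1.000 | 5.0% |
| 2.0 | 3.431 | 1.852 | 1.090 | 3.3% |

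**4. With drop-out and the AICC choice.** Each structure was fitted to the assumed covariance by expected Gaussian likelihood. Further assumptions: 204 subjects; 15% monotone drop-out, completely at random and even over weeks; four correlation shapes, namely AR(1) 0.90, AR(1) 0.95, CS 0.70, and 0.5 + 0.4 × 0.8^lag. The reported SE of the Week 12 contrast was compared with its sandwich SE, for the structure that AICC selects.

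| Assumed SD path to 1.7 | Ratio | Type I error |
|---|---|---|
| From 1.4, level by Week 4 | 0.938-0.967 | 5.8-6.6% |
| From 1.4, linear | 0.908-0.910 | 7.5% |
| From 1.1, linear | 0.819-0.826 | 10.6-10.9% |
| Flat | 1.000 | 5.0% |
| Falling from 2.0 | 1.094-1.096 | 3.2% |

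Example (AR(1) 0.90, linear from 1.1): reported SE 0.207 against a true 0.251. The ratio is 0.825, and 2Φ(−1.96 × 0.825) = 10.6%. A more extreme start of 0.8 with a linear rise gives 14.1-14.4%.

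In these scenarios TOEPH gives 5.0%, ARH(1) 4.8-5.0% and CSH 4.2-5.0%. With complete data CSH can fall to 3.6%.

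**5. Finite-sample check** (REML, AICC choice, AR(1) 0.90, 15% drop-out; 180 df in place of Kenward-Roger; no site or baseline term).
- Linear rise from 1.1, 328 trials: mean reported SE 0.207, empirical SD 0.249, type I error 11.6% (Monte Carlo SE 1.8 points). TOEPH gave 4.0% (1.1).
- Flat, 274 trials: selected structure 5.1% (1.3), TOEPH 5.8% (1.4).

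**The case against.** **The trigger is unlikely for the primary model.** UN was fitted to simulated data with 204 subjects, 20 assumed sites, a baseline covariate and SD rising from 1.1 to 1.7. It converged in 105 of 105 trials with 15% drop-out, 94 of 94 with 3% intermittent gaps added, and 86 of 86 with 30% drop-out plus gaps. These were small runs on Gaussian data and did not use PROC MIXED's optimiser, but they carry weight. SAP 6.2.16 also pools sites with fewer than 6 subjects, because small sites could give numbers "which could lead to convergence issues, unreliable treatment effect estimates and p-values". This objection stands and keeps the point minor. It does not remove it: the SAP provides for the contingency, and a prespecified fallback should be valid when it is used. Failure is more plausible in the subgroup MMRMs, where samples are smaller.

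**The weekly SDs are assumed.** True. Nothing in the documents supports a rise, and the largest figures need a steep one that continues to Week 12.

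**A discrepancy would be visible.** The supportive ANCOVA, "MODEL CFB_WEEK12 = TREATMENT SITE BASELINE / SOLUTION", estimates its own Week 12 variance, and weekly summaries will include SDs (SAP 6.3.4). Both would help a reader, but neither replaces the primary p-value.

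**A fixed order gives up the AICC choice of correlation shape.** Partly fair, since a wrong shape can bias the estimate itself under missing at random, which was not examined; nor was whether TOEPH converges when UN does not. But TOEPH contains ARH(1) and CSH as special cases, so a narrower shape is imposed only if TOEPH also fails.

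A reader might infer that the planned primary analysis has inflated type I error, or that any change of variance between weeks causes bias. The documents support neither. UN has no such constraint, and bias needs a Week 12 variance that differs from the pooled one. Nor is the pattern-mixture analysis shown to be compromised: its sample code states TYPE=UN and runs on completed data, where UN failure is less likely still. The tipping-point analysis runs only after a significant primary result.

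**Conclusion.** The point holds as a minor, conditional improvement. Two things must both happen for it to matter: UN fails to converge, and the Week 12 variance differs from the variance pooled over weeks. The documents establish neither. If both occur, the size depends on the assumed path of the weekly SD: from about one or two percentage points above nominal for a mild early rise to about double the nominal 5% for a linear rise from 1.1, with a conservative test if variance falls. The mechanism is certain, but the magnitudes rest on assumed SDs, the four correlation shapes and drop-out completely at random. The SAP rule is complete and unambiguous, and the sample size is unaffected. If UN converges, there is no effect.

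**What to change.** In SAP 6.11.1.2, replace the fallback with a fixed order. If UN does not converge, fit TOEPH, then ARH(1), then CSH, use the first that converges, and keep DDFM=KR. Only if all three fail, use the existing AICC choice among TOEP, AR(1) and CS, so that a prespecified structure always remains.

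State that the order applies to every 12-week MMRM: the primary analysis, the pattern-mixture and tipping-point refits, sleep interference, weekly acetaminophen dose, pain upon walking, worst pain, and the exploratory and subgroup MMRMs. The detailed text for some of these is not in the public SAP, so they are identified here from the table list in SAP 11.

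The cost is a sentence of wording and a change to the TYPE= option. Each heterogeneous structure has 11 more covariance parameters than its equal-variance counterpart, still far below UN's 78. CSH can be slightly conservative when correlation decays with lag, which is why it comes last of the three.
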